## Study Protocol and Statistical Analysis Plan

### Background

Women Veterans' (WVs) numerical minority in Veterans Health Administration (VA) healthcare settings has created logistical challenges to delivering gender-sensitive comprehensive primary care (PC). Women commonly must access an array of VA and non-VA providers, usually requiring multiple separate visits, to achieve the same basic level of care which male veterans can achieve through a single onsite PC visit [1–3]. The VA has invested in a variety of resources intended to improve WVs' care, establishing women's health clinics, designating Women's Health (WH) PC providers with the requisite training/experience, and contracting with non-VA obstetrics and gynecology services. Despite these investments, WVs' quality of care in VA continues to lag behind that of male veterans [4]. Contributing to these outcomes is the lack of gender sensitivity prevalent in many VA care settings, which may be linked to low WV retention rates in VA care [5, 6].

The VA has undertaken a major initiative to transform care through mandated implementation of Patient Aligned Care Teams (PACTs), which hold promise for addressing many of the gaps in WVs' care. The PACT model is based on the concept of patient-centered medical homes (PCMHs), widely endorsed by PC professional societies and shown to improve quality of care and patient, provider, and staff satisfaction, while reducing costs [7, 8]. PACT focuses on development of high-performing "teamlets" comprised of PC providers, nurses, and administrative support who together manage care of a defined panel of patients. These teamlets operate within a larger team that includes, for example, pharmacists, social workers, mental health (MH) providers, and dietitians, and link to specialists and hospital care in their medical "neighborhood." Through these teams/teamlets, PACT aims to achieve improvements in accessibility, continuity, coordination, and comprehensiveness using team-based care that is patient-driven and patient-centered [9]. These improvements, in turn, should translate into better chronic illness care and prevention and lower costs.

However, how VA should adapt this major reorganization to meet the needs of special populations, such as WVs, is yet to be fully worked out. The PACT model itself does not include specific accommodations for gender-specific care or improved gender sensitivity. Current WV care is also out of step with PACT priorities and emphasis on "one-stop shopping" for care [10]. For example, WVs are more likely to be outsourced to the community for gender-specific services now than they were 10 years ago, and, while the number of women's clinics is up, over 40 % do not deliver comprehensive PC [3]. Therefore, improving VA PC alone or "beefing up" women's clinics is unlikely to achieve what an integrated WH-PACT model must reconcile to improve care for WVs and thereby reduce persistent gender disparities in VA care [11, 12].

### Research aims

We propose to use evidence-based quality improvement (EBQI) in the context of the Chronic Care Model to develop and test achievement of WH-PACT in a cluster randomized trial [13, 14]. EBQI is a systematic approach to developing local research-clinical partnerships to produce tailored, evidence-based care models or redesigns [15]. The resulting WH-PACT redesign will make use of local WH resources (e.g., women's clinics, designated providers), while linking them to the broader PACT initiative and medical center resources. We will also explore the extent to which receiving care that meets WH-PACT tenets translates into higher

value (better quality, lower costs) for individual WVs, evaluate local implementation, and develop tools for sustaining and spreading WH-PACT. Our aims are:

1. To assess the effectiveness of EBQI for developing a WH-PACT model using a cluster randomized trial design. WH-PACT model achievement includes (a) PACT features (accessible, continuous, coordinated, team-based, patient-driven, and patient-centered), (b) comprehensive WH care (PC, gender-specific care, and integrated MH), and (c) gender-sensitive care delivery. We will (a) survey providers/staff on achievement of WH-PACT model attributes, (b) survey WV patients on WH-PACT model care experiences, and (c) analyze WH-PACT achievement (e.g., continuity) using secondary data.
2. To examine impacts of receipt of WH-PACT concordant care on WVs' outcomes. We will explore impacts on quality of chronic disease care and prevention, health status, utilization and costs.
3. To evaluate the processes of EBQI-supported WH-PACT implementation. We will assess pre-post practice contexts; document EBQI activities and their relationship to provider/staff and team actions and attitudes; document WH-PACT implementation; and examine barriers and facilitators to EBQI -supported WH-PACT implementation using mixed methods (e.g., semi-structured interviews, brief progress narratives).
4. To develop implementation and evaluation tools for use in EBQI-supported WH-PACT model adaptation, implementation, sustainability, and spread to additional VA facilities.

## **Methods/design**

### **Setting, site selection, trial design, and participants**

The VA healthcare system is currently organized into 21 regional Veterans Integrated Service Networks (VISNs), with administrative and clinical authority over VA medical centers (VAMCs) and their affiliated programs in geographically distinct regions of the USA [16]. Study sites are members of the VA Women's Health Practice-Based Research Network (WH-PBRN), a 37-VAMC network spanning 17 VISNs and comprising over 270 geographically distinct sites of care and nearly 600 designated WH providers [17]. Together, PBRN facilities serve over 100,000 WVs (about one third of WVs seen in VA) and span diverse patient populations. We identified five VISNs with three or more WH-PBRN sites; we excluded one that was already participating in a VISN-wide EBQI stepped-wedge trial. We approached leadership at the other four VISNs and their WH-PBRN member site leads about study participation. All agreed to participate. One VISN dropped out ahead of randomization, which was replaced with a VISN that had two WH-PBRN sites; we then worked with VISN leadership to identify a third non-PBRN VAMC, which subsequently joined the WH-PBRN (since the trial began, the WH-PBRN has expanded to 60 VAMCs in 20 of 21 VISNs). VAMCs participating in the trial span nine states (Connecticut, Illinois, Iowa, Massachusetts, Minnesota, North Dakota, Pennsylvania, West Virginia, and Wisconsin).

This study is designed as a parallel two-arm, cluster randomized controlled trial (cRCT), blocked on VISN (Fig. 1). We randomly assigned the 12 VAMCs to EBQI or usual PACT implementation in an unbalanced 2:1 ratio within VISN, supporting appraisal of variations in EBQI implementation in the context of differences of VISN geography, resources, and oversight (Fig. 1). No site stratification or matching criteria were used. The study biostatistician used [www.randomization.com](http://www.randomization.com) with a randomized permuted block of three (simple block of three

VAMCs within each VISN) and a seed of 15,356 to start the random allocation sequence. The eight intervention VAMCs will engage in EBQI, while the four control VAMCs will receive standard PACT and WH care delivery handbooks and guidance that all VA facilities receive. The study biostatistician assigned the VAMCs to EBQI or control, while the study PI ([name]) enrolled and launched EBQI with the resulting eight VAMCs.

Local quality improvement (QI) teams, their WH and PC leaders, and VAMC facility leadership, as well as VISN leaders and other key stakeholders (e.g., national VA partners), will be the focus of this study, given their varying levels of responsibility for WH, primary care, and PACT implementation. Outcomes for the PC providers and WVs seen in each participating VAMC's primary care/PACT programs, whether sited in a women's clinic or general primary care clinic, will also be examined.

### **Ethical approval and informed consent**

The VA supports a large number of Institutional Review Boards (IRBs) across the USA among chiefly academically affiliated VAMCs, in addition to a Central IRB (cIRB) for multisite research. While this study represents a 12-VAMC cluster randomized trial, the cIRB determined that participating sites were not engaged in research (i.e., the intervention is QI, and all research activities are performed centrally at the Principal Investigator's site in the VA Greater Los Angeles (GLA) Healthcare System), permitting the use of the local GLA IRB. Evaluation and data collection activities are submitted serially to the GLA IRB for review as discrete human subject research component projects (e.g., patient survey component, provider/staff survey component). Two components involved contractors at local affiliates (teamlet interviews with UCLA, provider/staff survey with RAND Health), whose IRBs also reviewed and approved their respective activities. The study is registered with ClinicalTrials.gov (NCT02039856).

### **VA partnerships**

This study is one of the five inter-related projects that together comprise a WH-focused research-clinical partnership funded by VA Health Services Research and Development (HSR&D) Service under the Collaborative Research to Enhance and Advance Transformation and Excellence (CREATE) initiative [18]. Central to CREATE is the involvement of policy and/or practice partners in the design, conduct, and dissemination of study results, with an emphasis on implementation and spread of successful strategies. Within the VA Office of Patient Care Services, Women's Health Services (WHS) is the WH CREATE's primary partner, with close involvement of Mental Health Services (MHS) in assessing within- and across-project mental health analyses and themes. The WH CREATE is also advised by an Executive Steering Committee, comprised of WHS and MHS partners, representatives in national VA clinical quality reporting, regional network leadership, public affairs, WH clinical care delivery, WH policy, and implementation science and economics, as well as WVs who use the VA for care.

### **Conceptual framework for application of EBQI**

This study is guided conceptually and practically by the Chronic Care Model (CCM) [19]. Developed more than a decade ago, the CCM has been widely adopted to help guide clinical QI initiatives in the context of practices or teams in the USA and abroad [20]. The CCM depicts the health system linked with complementary community resources, while providers and teams within each healthcare organization (regardless of size) aim to deliver care that is characterized by consistent, evidence-based assessment, treatment, and follow-up, with clinical

decision support (often via information technology) and support for patient self-management [21]. Applied to EBQI, local QI teams work on improvement plans that consider one or more CCM elements.

The CCM is a particularly strong fit for QI around medical homes, with an easy crosswalk to PACT goals. For example, for care coordination, PACT teamlets should link patients with community resources to facilitate referrals and respond to social service needs; provide care management services for high-risk patients; integrate behavioral health and specialty care through structured collaboration, co-location, or referral protocols; track and support patients when they obtain services outside the practice; follow up with patients within a few days of an emergency room visit or hospital discharge; and communicate test results and care plans to patients/families [22].

Addressing CCM elements, however, requires substantial stakeholder buy-in, local knowledge and skills in QI, availability of needed technical support, and continual guidance. Previous research has shown that evidence-based programs require adaptation to organizational values, needs, and resources prior to dissemination [23]. More structured than continuous quality improvement (CQI), which has had mixed results, EBQI is a systematic approach to developing a multilevel research-clinical partnership approach to QI, using top-down/bottom-up features to engage senior organizational leaders and local QI teams in implementing improvements in the context of prior evidence, provider behavior change methods, and local practice structure and resources [24]. National strategic directives serve as guides, while regional expert panels set innovation design priorities [25]. Local interdisciplinary QI teams design and implement local activities, while researchers serve as technical experts and guides. EBQI also uses team-based CQI methods to help teams structure their aims and measures and conduct plan-do-study-act (PDSA) cycles, in addition to convening topic-focused workgroups with research/clinical expertise with periodic across-site meetings for training and sharing data and lessons learned. EBQI's value-added contribution is an emphasis on (a) applying objective evidence, with (b) theory review and synthesis integrated into aspects of innovation design and implementation, (c) valid and reliable measurement, and (d) formal measurement feedback to stakeholders at all levels [26]. Effectively applied to a series of VA implementation studies [27–29], EBQI uses well-established implementation strategies, such as local priority setting among key stakeholders, adaptation of the evidence to local context (practice tailoring), audit-and feedback of QI data to support rapid cycle improvements, and practice facilitation to support implementation into practice [30].

### **EBQI implementation strategies applied to WH-PACT and hypotheses**

In this study, we propose to use EBQI to convene multilevel stakeholder panels (presenting panels with evidence on factors associated with improved WH care in the context of national VA WH policy); facilitate local practice QI team design meetings, while providing QI training/ education and iterative QI data feedback; and sponsor within and across-practice QI collaboration calls (Fig. 2). We will continually foster coverage of CCM elements. We hypothesize that the initial results of EBQI will be the specification of the design choices for WH-PACT implementation, conduct of local QI activities, and improved provider/staff (and team) QI orientation, WH knowledge and attitudes, and gender awareness. We further hypothesize that EBQI will lead to higher achievement of WH-PACT (more practices achieve more features) in EBQI vs. control practices (aim #1). We anticipate that practice context (e.g., local leadership support, pre-EBQI factors) will moderate the relationships between EBQI and

implementation of WH-PACT. We will then explore the extent to which receipt of WH-PACT concordant care (PACT features, comprehensive WH care, gender sensitive care delivery) is associated with improved WH-PACT outcomes (aim #2).

For aim #3 (processes), we will document EBQI activities among intervention practices and examine barriers and facilitators to WH-PACT achievement in all participating practices. For aim #3, we will also rely on Diffusion of Innovation theory [31, 32] to frame our assessment of EBQI-supported WH-PACT adaptation, implementation, and sustainability, considering, for example, the trialability, complexity, and relative advantage of EBQI supported WH-PACT, as well as concordance between WH-PACT achievement and CCM principles. Aim #4 (tools) will build on our conceptual model and benefit from our practical experience implementing evidence-based care models [15].

In this study, EBQI implementation will focus on six main activities: (1) conduct of four VISN-level interdisciplinary stakeholder planning meetings using expert panel techniques to come to consensus on PACT QI priorities for women Veterans (“QI roadmaps”); (2) development and training of a local QI champion and QI team members at EBQI-assigned VAMCs to pursue one or more QI projects from the “roadmaps”; (3) formative feedback from patient, provider, staff, and practice survey data; key stakeholder and teamlet interview data; and utilization and cost-related administrative data; (4) ongoing practice facilitation and expert review and feedback on local QI proposals and progress; (5) monthly across-intervention VAMC calls to facilitate collaboration and spread of effective QI innovations; and (6) technical work groups designed to provide additional evidence-based support in priority areas (Table 1).

## **Evaluation**

As shown in Fig. 3, we have planned a comprehensive approach to evaluating the processes and outcomes of EBQI for tailoring PACT to the needs of WVs. Baseline data collection (as well as 12-month follow-up in the case of the patient surveys) will be used for formative feedback to EBQI-assigned VAMCs. Table 2 provides an overview of the data sources, samples, and measures planned for each evaluation component.

## **Sample size calculation and power analysis**

We based our power calculations on the study’s unequal (2:1) intervention-to-control ratio and clustered sample design. To detect a moderate (0.20) effect size between WVs at intervention and control sites, we considered data from the Primary Care Satisfaction Survey for Women’s Care Coordination and Comprehensiveness scale, [33] with 12 practices (8 intervention-to-4 control sites), cluster adjustment ( $ICC = 0.03$ ) [34], and two-tailed 5 % significance level. Based on these parameters, we will target enrollment of a minimum of 40 WVs at each of the 12 study sites over the 2-year period (baseline to 24-month follow-up), for a total of 480 WVs who complete a baseline and at least one of the two follow-up surveys (12- and/or 24-month). To achieve this target, we will create a baseline sample of 6665 WVs who have received PC or WH care at one of the study’s 12 participating sites during the 12-month period prior to the baseline survey (555 per site). Allowing for a conservative 20 % response rate and 40 % attrition over the 2-year period, we aim to enroll 111 WVs at each of the 12 sites at baseline, for a total of 1333 interviews at the completion of the first wave.

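### The 0.20 effect size behind 40 women per site has no metric, power level or baseline correlation; in SD units the stated inputs give 80% power for about 0.40, not 0.20

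*Combined protocol and SAP*

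**What the plan says.** The section *Sample size calculation and power analysis* bases its calculation on the "unequal (2:1) intervention-to-control ratio and clustered sample design". The aim is "To detect a moderate (0.20) effect size between WVs at intervention and control sites", on a care coordination and comprehensiveness scale from a women's primary care satisfaction survey, "with 12 practices (8 intervention-to-4 control sites), cluster adjustment" at ICC 0.03, and a two-tailed 5% level. It then concludes: "Based on these parameters, we will target enrollment of a minimum of 40 WVs at each of the 12 study sites", "for a total of 480 WVs who complete a baseline and at least one of the two follow-up surveys".

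The section does not give a power level, the units of 0.20, an SD for the scale, or a correlation between baseline and follow-up scores. No other section supplies them.

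Three other sections bear on the point:
- *Setting, site selection, trial design, and participants*: "This study is designed as a parallel two-arm, cluster randomized controlled trial (cRCT), blocked on VISN", with three sites per VISN.
- *Primary outcome measures*: the outcome is expressed as changes in levels of PACT features.
- *Statistical analyses*: regression adjusted for covariates and clustering. The patient-level controls listed are sociodemographics, health status, comorbidity and utilization. The baseline score is not named.

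**The concern.** A reader who meets an effect size of 0.20 in a two-group comparison of a scale will normally take it as 0.20 SD. On that reading, 480 women in 12 clusters look too few. With only four control sites, between-site variance also limits what extra women per site can achieve.

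This is the only quantified statement of sensitivity in the plan. If it is taken as 0.20 SD, a null result on the scale could be read as evidence against an effect of that size, although the design may be unlikely to detect it. If 0.20 means something else, the reader is never told the target difference in SD units, and the two readings can differ about twofold.

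**Working it through.** **Inputs from the sample size section:** 8 and 4 sites, m = 40 women per site, ICC 0.03, two-sided 5%, effect 0.20. **Assumptions, not in the documents:** 0.20 in SD units, an 80% power level where used, all correlations, and the t reference. The df are 12 − 2 = 10 ignoring VISN, or 10 − 3 = 7 with four VISN blocks removed. The 7-df figures take no credit for variance that blocking might remove.

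**1. Reproducing the plan's figure.** The target of 40 per site cannot be derived from the stated inputs alone, because power and metric are missing. Steps 2 to 5 show what it does and does not match.

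**2. Power for 0.20 SD, unadjusted, one follow-up.**
- Var = (1/8 + 1/4) × [0.03 + 0.97/40] = 0.375 × 0.05425 = 0.02034; SE = 0.1426.
- 0.20/0.1426 = 1.402. Normal power = Φ(1.402 − 1.960) = 0.289.
- Noncentral t: 0.246 (10 df), 0.229 (7 df).

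**3. Ceiling with unlimited women per site.** SE tends to √(0.375 × 0.03) = 0.1061. Power is 0.470 (normal), 0.400 (t, 10 df) or 0.371 (t, 7 df).

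**4. Detectable effect at an assumed 80% power, m = 40.** Normal: (1.960 + 0.842) × 0.1426 = 0.400 SD. Noncentral t: 0.444 SD (10 df), 0.466 SD (7 df).

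**5. What 40 per site matches.** For 0.40 SD, normal power is 79.6% at m = 39 and 80.1% at m = 40, so 40 is the smallest number reaching 80%. With t it is 72% (10 df) or 67% (7 df).
- Cohen's f = 0.20 with the equal-group conversion is d = 2 × 0.20 = 0.40, which recovers 40 per site. The 2:1 conversion gives d = 0.20/√(2/9) = 0.424, which needs 32 per site (normal).
- A raw difference of 0.20 points matches if the scale SD is about 0.20/0.40 = 0.50 points. The documents give no SD.

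**6. Role of clustering.** With ICC 0 and no adjustment, SE = √(1/320 + 1/160) = 0.0968 and power for 0.20 SD is 54%. With ICC 0 and an assumed baseline correlation of 0.7, SE is multiplied by √0.51 and power is 82%.

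**7. Baseline adjustment at ICC 0.03, assumed correlation 0.7 at site and patient level.**
- One follow-up: SE = 0.1426 × √(1 − 0.49) = 0.1019. Power for 0.20 SD is 50% (normal) or 42% (t, 9 df, one further df for the covariate). The 80% detectable effect is 0.285 or 0.321 SD.
- Both follow-ups averaged, all women giving both (optimistic): the variance factor is (1 + 0.7)/2 − 0.49 = 0.36, so SE = 0.0856. Power is 65% or 55%; detectable effect 0.240 or 0.270 SD.

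**8. Retention.** The section says "Allowing for a conservative 20 % response rate and 40 % attrition over the 2-year period". Applied once to 1333 baseline interviews, 40% attrition leaves 799.8, or about 67 per site. Unadjusted power for 0.20 SD is then 34% (normal), 29% (t, 10 df) or 27% (t, 7 df).

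**The case against.** The strongest reply is that 40 per site was computed correctly in a metric the text forgot to name. Step 5 supports this: 40 is the exact answer for 0.40 SD at 80% power. That match is an inference, since neither Cohen's f nor raw points is mentioned, but it stands. It rules out inferring that 480 is an arithmetic error. No power is stated, so 23 to 29% contradicts no figure in the plan.

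A second reply is that no section plans an unadjusted comparison at one follow-up. The plan speaks of changes, covariate adjustment and two follow-up waves, and its list of controls need not be exhaustive. This also stands, so a reader should not infer that the trial itself has 23 to 29% power. Power under the planned analysis cannot be determined from the documents. But the sample size section takes no credit for baseline information, and at assumed correlations of 0.7 with one follow-up the figure for 0.20 SD is still only 50% or 42%.

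A third tempting inference is that the shortfall holds whatever the ICC. It does so only without adjustment: step 6 gives 54% unadjusted but 82% with an assumed correlation of 0.7.

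Finally, the analysis section specifies neither 10 nor 7 df, so the t results are a range around the normal figure.

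**Conclusion.** The calculation is under-specified. On the ordinary SD reading, its inputs do not support 0.20. For an unadjusted comparison at one follow-up, power for 0.20 SD is 29% (normal), 25% (t, 10 df) or 23% (t, 7 df), capped at 47% (normal) by the 12 sites. The effect detectable with an assumed 80% power is about 0.40 SD, or 0.44 to 0.47 SD with a t reference.

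That detectable effect depends only on the number of sites, women per site, ICC, significance level and assumed power. It therefore holds whether 0.20 was a slip, Cohen's f or scale points. What remains open is which of these was meant and how much credit, if any, was intended for baseline scores or repeated follow-up. The point should be fixed for interpretation: the timeframe section shows that local QI and the baseline surveys had already started, and nothing here calls for a different enrolment.

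**What to change.** Leave enrolment and sites unchanged.

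- *Sample size calculation and power analysis*: replace the 0.20 statement with wording such as: with 8 and 4 sites, 40 women per site, ICC 0.03 and a two-sided 5% level, an unadjusted comparison at one follow-up has 80% power for about 0.40 SD (0.44 to 0.47 SD with a t reference on 10 or 7 df). State the metric of 0.20 and the power level behind 40 per site. If it was Cohen's f or raw points, say so and give the SD equivalent.
- *Statistical analyses*: name the baseline score as a covariate. It is already being collected.
- If power credit is taken for baseline adjustment, change scores or both follow-ups, give the assumed site-level and patient-level correlations and the resulting detectable effect. For example, 0.7 at both levels gives about 0.29 to 0.32 SD with one follow-up.

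The cost is a few sentences and, if 0.20 meant SD units, a less favourable stated sensitivity. No extra women, sites or data collection are needed.
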